1 PROTOCOL SUMMARY

[figure not shown]
1.1 SYNOPSIS

Title:	Shark Mouth Modified Pancreaticojejunostomy (SMMP) in Pancreaticoduodenectomy Procedure
Study Description:	We established a new digestive reconstruction technique named SMMP, which had theoretical advantages including easier performed; lower tension and less complication. The pancreaticojejunostomy time, post-operation complication, mortality and hospital stay will be documented to study the safety, efficiency and advantage of this new procedure.
Objectives:	Primary Objective: To evaluate the new procedure (SMMP) Secondary Objectives: To popularize SMMP
Endpoints:	Primary Endpoint: pancreatic fistula Secondary Endpoints: Mortality ; Morbidity ; pancreaticojejunostomy time ; Hospital stay
Study Population:	120 cases of Chinese Patients diagnosed with pancreatic cancer or other diseases which need pancreaticoduodenectomy; any gender; 18-80 years old
Phase:	N/A
Description of Sites/Facilities Enrolling Participants:	Department of General Surgery, Peking University Third Hospital
Description of Study Intervention:	The remnant of jejunum is closed by continuous suture. The transverse incision is made on the posterior wall of the jejunum (5 centimeters distal to remnant), which starts at 0.2 centimeter to the mesenteric border and should never exceed the anti-mesenteric border. In case of large pancreas remnant, a longitudinal jejunum incision will be done at anterior part of anastomosis. The posterior part of anastomosis is two layers of intermittent suture, including seromuscular suture layer and full thickness suture layer. The anterior part of anastomosis is a single layer full thickness suture. At last, the seromuscular layer of the proximal jejunum is sutured with the anterior pancreatic capsule to cover the anterior part of anastomosis.
Study Duration:	December, 2017 To December, 2019
Participant Duration:	3 months

1.2 SCHEMA

*This section should include a diagram that provides a quick “snapshot” of the study and ideally be limited to 1 page. Below are examples of schematics that show the level of detail needed to convey an overview of the study design. Depending on the nature of your study, one example may be more appropriate than another. Regardless, the examples included here are intended to guide the development of a schematic that is appropriate to the planned study design and will need to be customized for the protocol. Revise with study-specific information and adapt the diagram to illustrate your study design (e.g., changing method of assignment to study group, adding study arms, visits, etc.). The time point(s) indicated in the schematic should correspond to the time point(s) in **Section 1.3, Schedule of Activities**, e.g., Visit 1, Day 0; Visit 2, Day 30 ± 7; etc.*

Process diagram

1.3 SCHEDULE OF ACTIVITIES (SOA)

	Screening Day -7 to -1	Operation Visit 1, Day 0	Visit 2 Day 1	Visit 3 Day 3	Visit 4 Day 7	Final Visit 5 Day 90 +/-3 day
Procedures						
Informed consent	X					
Demographics	X					
Medical history	X					
Physical exam (including height and weight)	X	X	X	X	X	X
Vital signs	X	X	X	X	X	X
Performance status	X	X	X	X	X	X
Hematology	X	X	X	X	X	X
serum chemistry ^a	X	X	X	X	X	X
Pregnancy test ^b	X					
Trial intervention		X				
Intraoperative outcomes ^c		X				
drainage quality			X	X	X	X
drainage quantity			X	X	X	X
drainage amylase			X	X	X	
drainage bacteria culture			X	X	X	
Adverse event review and evaluation		X	X	X	X	X
Complete Case Report Forms (CRFs)	X	X	X	X	X	X

a:Albumin, alkaline phosphatase, total bilirubin, bicarbonate, BUN, calcium, chloride, creatinine, glucose, LDH, phosphorus, potassium, total protein, AST, ALT, sodium.

b:Urine pregnancy test (women of childbearing potential).

c: pancreaticojejunostomy time; operative course, final pathology, gland texture, pancreatic duct diameter, size of the stent, length of pancreatic juice in the stent tube, width of the pancreatic stump and diameter of the jejunum

2 INTRODUCTION

2.1 STUDY RATIONALE

Pancreaticoduodenectomy (PD) is one of the most complicated surgical procedure and one of the standard treatments for benign and malignant disease of pancreatic head and periampullary region. The key point of PD is still the enteric reconstruction of pancreatic stump. We established a new digestive reconstruction technique named shark mouth modified pancreaticojejunostomy, which had theoretical advantages including easier performed; lower tension and less complication. So we conduct this trial to evaluate this procedure.

2.2 BACKGROUND

Pancreaticoduodenectomy (PD) is one of the most complicated surgical procedure and one of the standard treatments for benign and malignant disease of pancreatic head and periampullary region. Improvements in surgical techniques and the perioperative management of patients undergoing PD have reduced the surgical mortality rates to less than 3% in high-volume medical centers. However, the incidence of postoperative complication remains high, which ranges from 30% to 50% and the pancreatic fistula rate ranges from 5% to 40%.

Since the ISGPF classification was declared in 2005, it has been widely accepted. The rate of clinically relevant postoperative pancreatic fistula (CR-POPF) continued to persist at approximately 15%. The CR-POPF is one of the most important life-threatening complications that could lead to intra-abdominal abscess, hemorrhage, and sepsis. The exocrine output from the pancreatic remnant was now widely implicated as the initial cause of fistula. The underlying process is the continuous leakage of caustic proteases and lipolytic enzymes, with significant local consequences (abscess, pancreatic fistula, acute pancreatitis, pseudoaneurysm) and systemic sequelae (sepsis, shock, pulmonary insufficiency). So the clinically significant pancreatic fistula symptoms were caused by enzyme leakage and inflammation including bacterial and non-bacterial inflammation. The enzyme may be the initial promoting factor but the inflammation facilitated by enzyme was another important factor in the development of pancreatic fistula. The higher body weight, undilated main pancreatic duct and soft gland were widely accepted as the risk factors of CR-POPF and all these patient factor couldn't be changed by the surgeons. So the feasible and easy way to decrease the CR-POPF is to improve the enteric reconstruction technique of pancreatic stump.

There were different techniques of enteric reconstruction, including: invagination pancreaticojejunostomy, binding pancreaticojejunostomy, duct-to-mucosa pancreaticojejunostomy, Roux-en-Y pancreaticojejunostomy, and pancreaticogastrostomy and each technique had its advantages and disadvantages. Several anastomotic surgical techniques have been developed to reduce the incidence of pancreatic fistula in recent decades, including, Peng's binding method, Bulgart Method. Large prospective studies and meta-analyses show no significant differences in postoperative complications and mortality among these reconstruction methods. Invagination pancreaticojejunostomy and duct-to-mucosa pancreaticojejunostomy are the most popular technique of pancreaticojejunostomy. However invagination pancreaticojejunostomy is difficult to perform in the situation of larger pancreatic remnant and soft gland. Duct-to-mucosa pancreaticojejunostomy is difficult to perform in the situation of thinner pancreatic duct and the uncompleted drainage of the pancreatic remnant is also considered to be the important reason of CR-POPF.

Theoretically, the incision of "Shark Mouth" might facilitate the pancreaticojejunostomy especially for the large pancreatic remnant; the feature of anastomosis might reduce the tension of pancreaticojejunostomy, which is important for the healing of anastomosis and might reduce the risk of POPF in the soft pancreas; the characters of anastomosis permits total drainage of pancreatic remnant, which is crucial in the situation of thinner pancreatic ducts. The purpose of this study is to evaluate the new anastomosis called "Shark Mouth Modified Pancreaticojejunostomy", especially the morbidity of POPF.

2.3 RISK/BENEFIT ASSESSMENT

2.3.1 KNOWN POTENTIAL RISKS

The main risks for study patients are the occurrence of postoperative pancreatic fistula and other complications after the performance of the shark mouth modified pancreaticojejunostomy. The rest potential risks are related with the rest clinically established standard surgical procedures.

2.3.2 KNOWN POTENTIAL BENEFITS

The main potential benefit for study patients is reducing the occurrence of postoperative pancreatic fistula as well as other complications after the performance of the shark mouth modified pancreaticojejunostomy. All rest surgical procedures carried out are clinically established standard procedures.

2.3.3 ASSESSMENT OF POTENTIAL RISKS AND BENEFITS

The newly established digestive reconstruction technique named shark mouth modified pancreaticojejunostomy has theoretical advantages including easier performed lower tension and less complication. Thus we performed the current clinical trial to investigate the clinical efficacy of the shark mouth modified pancreaticojejunostomy.

3 OBJECTIVES AND ENDPOINTS

OBJECTIVES	ENDPOINTS	JUSTIFICATION FOR ENDPOINTS
Primary		
To evaluate the new procedure shark mouth modified pancreaticojejunostomy (SMMP)	Postoperative pancreatic fistula (POPF) occurrence rate.	Postoperative pancreatic fistula (POPF) is one of the most frequent and ominous complications after PD, which is somehow related with the anastomosis technique
Secondary		
To popularize SMMP.	Anastomosis time Morbidities besides the POPF	

OBJECTIVES	ENDPOINTS	JUSTIFICATION FOR ENDPOINTS
	Postoperative hospital stay	

4 STUDY DESIGN

4.1 OVERALL DESIGN

This study is a prospective observational study evaluating the clinical efficacy of shark mouth modified pancreaticojejunostomy. The study will enroll a total of 120 participants who need to undergo the pancreaticoduodenectomy and will last for 2 years. The patients will undergo the shark mouth modified pancreaticojejunostomy procedure and be followed up. The primary endpoint of the study is the incidence of postoperative pancreatic fistula. The secondary endpoint is the postoperative hospital stay, morbidity, and the anastomosis time of the pancreaticojejunostomy procedure.

4.2 END OF STUDY DEFINITION

The end of the study is defined as completion of the last visit at 3 months after the operation.

5 STUDY POPULATION

5.1 INCLUSION CRITERIA

Patients who meet the following criteria will be included in the study:

1. Patients diagnosed with pancreatic cancer or other diseases which need pancreaticoduodenectomy
2. Operation-tolerated
3. Informed consent

5.2 EXCLUSION CRITERIA

An individual who meets any of the following criteria will be excluded from participation in this study:

1. History of abdominal operation
2. Pancreaticoduodenectomy is given up during operation

3. Patients require to exit from the study anytime
4. Pregnancy

5.3 SCREEN FAILURES

Screen failures are defined as participants who consent to participate in the clinical trial but are not subsequently assigned to the study intervention. A minimal set of screen failure information is required to ensure transparent reporting of screen failure participants, to meet the Consolidated Standards of Reporting Trials (CONSORT) publishing requirements and to respond to queries from regulatory authorities. Minimal information includes demography, screen failure details, eligibility criteria, and any serious adverse event (SAE).

5.4 STRATEGIES FOR RECRUITMENT AND RETENTION

Posters will be displayed in the outpatient and inpatient departments of Peking University Third Hospital in order to enroll the potential participants. The brief introduction of the clinical trial and the contact information will be printed on the posters.

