9.2 SAMPLE SIZE DETERMINATION

Sample size calculation is based on the primary endpoint: POPF rate. An assumed absolute risk of 10% difference in POPF occurrence is the appropriate basis for the calculation assuming 10% POPF in the SMMP technique group and 20% in the previous published data (Harnoss JC, Ulrich AB, Harnoss JM et al (2014) Use and results of consensus definitions in pancreatic surgery: a systematic review. *Surgery* 155:47-57). This calculation yields a total of 108 patients in the SMMP technique group, which assures a power of 80 % at a two-sided level of significance of 5 % (NCSS and PASS 11 (NCSS Statistical Software, Kaysville, UT, USA)). Assuming an expected withdrawal rate of 10 % during the trial, 12 additional patients will be included; therefore, the total sample size required is n = 120 patients.

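### With posters as the only stated recruitment route and a screening record that starts at consent, the protocol neither requires nor can verify a consecutive series

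*Protocol*

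**What the plan says.** Section 5.4 of the Protocol has one statement on how patients reach the study: "Posters will be displayed in the outpatient and inpatient departments of Peking University Third Hospital in order to enroll the potential participants". It adds that the posters carry a short description and contact information. It does not say that posters are the exclusive route, but it states no other.

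Section 5.3 sets where the record of non-entrants begins: "Screen failures are defined as participants who consent to participate in the clinical trial but are not subsequently assigned to the study intervention". The section gives CONSORT reporting as one of its aims.

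Section 4.1 describes the design: "This study is a prospective observational study evaluating the clinical efficacy of shark mouth modified pancreaticojejunostomy". All 120 participants are to have the new anastomosis, and there is no concurrent group. Section 9.2 takes its reference from the literature, "assuming 10% POPF in the SMMP technique group and 20% in the previous published data". Section 9.4.2 limits the primary result to the incidence of POPF among study participants.

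Section 2.2 names higher body weight, an undilated main duct and a soft gland as accepted risk factors for clinically relevant fistula. It gives a range of 5% to 40% for published fistula rates.

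**The concern.** A single-group rate set against an outside figure can be interpreted only if the reader knows how the group was drawn from the patients who could have been in it. The usual safeguard is a consecutive series with a count of everyone operated on. This protocol has neither. A PD patient who was not approached, who declined, or who had another reconstruction outside the study leaves no trace.

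By the protocol's own account in section 2.2, fistula risk varies with patient features. Body weight is known before consent, and duct width may be visible on preoperative imaging. If entry depends on such features, the observed rate reflects case mix as well as technique. The final report could not state what share of the department's PDs the participants represent. This is separate from whether 20% is the right benchmark, because a better benchmark would not repair selection at entry.

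**Working it through.** **1. The plan's own figure.** Inputs from section 9.2: reference rate p0 = 0.20, expected rate p1 = 0.10, and a sample size that "assures a power of 80 % at a two-sided level of significance of 5" per cent. For one proportion against a fixed reference (normal approximation):

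n = [1.960 × √(0.20 × 0.80) + 0.842 × √(0.10 × 0.90)]² / (0.20 − 0.10)² = 107.4, so 108.

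With 10% withdrawal, 108 / 0.90 = 120. Both stated figures reproduce, so there is no arithmetic error. The calculation does treat participants as exchangeable with the population behind the published 20%.

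**2. A yardstick.** With 108 patients, an exact binomial test against 20% rejects on the low side at 13 or fewer events (13/108 = 12.0%). The probability of this is 0.021 if the true rate is 20% and 0.81 if it is 10%. Section 9.4.2 plans only to report the incidence. The limit of 13 is therefore what the sample size calculation implies, not a test the protocol specifies.

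**3. Effect of selection at entry.** These assumptions are not in the documents:
- The technique has no benefit, so the rate across all the department's PD patients is 20% whichever anastomosis is used.
- A fraction f is enrolled.
- Those not enrolled have RR times the risk of those enrolled.

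Then the expected enrolled rate = 0.20 / [f + (1 − f) × RR].

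| f | RR | Expected enrolled rate | Chance of ≤13 of 108 |
|---|---|---|---|
| no selection | – | 20% | 0.021 |
| 0.9 | 1.5 | 0.20/1.05 = 19.0% | 0.036 |
| 0.8 | 2 | 0.20/1.20 = 16.7% | 0.12 |
| 0.7 | 2 | 0.20/1.30 = 15.4% | 0.21 |

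**4. The other direction.** If harder cases are preferentially enrolled, RR is below 1. With f = 0.8 and RR = 0.5, the rate is 0.20/0.90 = 22.2%, so selection would count against the technique.

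**5. What selection cannot do.** For the enrolled rate to be 10% with 20% overall, the non-enrolled rate would have to be (0.20 − 0.10f)/(1 − f). That is 43% at f = 0.7, 60% at f = 0.8 and 110% at f = 0.9, which is impossible. Mild selection cannot alone produce the planned halving.

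**The case against.** The strongest reply is that the point rests largely on silence. Posters are not declared exclusive, and the department may well invite every patient. Section 10.1.1.2 has the investigator explain the study to each participant. This stands as far as it goes: consecutive enrolment is not ruled out. But it is not required either, and no planned record would confirm it.

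Second, part of the problem is already covered. Consent falls in the screening window, days −7 to −1. Gland texture and duct diameter are listed in section 1.3 as intraoperative outcomes. A consented patient who is then given a different anastomosis meets the section 5.3 definition and is logged. Case mix among participants will also be visible, and section 9.4.6 plans subgroups by texture, duct diameter and disease. This stands and narrows the gap to selection before consent. It does not supply the denominator or any description of those left out.

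Third, the direction is unknown. Section 2.2 promotes the technique especially for large remnants, soft glands and thin ducts, so enrolment could just as well favour difficult cases. This stands.

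A reader might also take the inclusion criterion "Operation-tolerated" as a lever for steering hard cases away. The documents do not support that. A patient unfit for surgery has no PD at all and so is not a missed operated case, and fitness is not among the risk factors named in section 2.2.

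**Conclusion.** The concern holds as a weakness of design and conduct: the series is neither required to be consecutive nor verifiable as such, in a study whose result is read against an external 20%. Recruitment and screening rules belong in the protocol, so this is not a matter left to a statistical analysis plan.

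The size is a sensitivity range and not a finding. It rests on no treatment benefit, 20% overall, and assumed values of f and RR. Over that range, selection lowers the expected rate by 1.0 to 4.6 percentage points (20% to 19.0% and to 15.4%) and raises the chance of an apparently favourable result from 0.021 to between 0.036 and 0.21.

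Two stronger readings are tempting. One is that selection occurs here and flatters the technique; nothing in the documents shows that it occurs or in which direction. The other is that a definite part of the planned 10-point difference can be put down to selection. The documents give neither the number of PDs done nor the rate in patients not enrolled. If those patients had another anastomosis, a higher rate among them would mix selection with technique. Extreme assumptions (half enrolled, three times the risk in the rest) do give 0.20/2.0 = 10% and a chance of 0.81, but no figure in the protocol makes them likely.

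**What to change.** - **Section 5.4:** state that every patient scheduled for PD in the department is screened and, if eligible, invited consecutively. Keep posters as a supplement.
- **Section 5.3:** extend the record to an anonymous count of all PDs done in the period, with eligibility, reason for non-enrolment and anastomosis used. Where ethics approval allows, add body weight, duct diameter and gland texture. Without these the log gives a denominator but cannot show whether those left out differed in risk.
- **Reporting:** show enrolled, eligible and all PDs in the flow chart.

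The sample size, visits and operation do not change. The cost is a short protocol change, one line of data per operation, and ethics committee agreement to hold data on patients who are not participants.

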6 STUDY INTERVENTION

6.1 STUDY INTERVENTION(S) ADMINISTRATION

6.1.1 STUDY INTERVENTION DESCRIPTION

The SMMP will be performed according to the standard procedure. The remnant of jejunum is closed by continuous suture. The transverse incision is made on the posterior wall of the jejunum (5 centimeters distal to remnant) , which starts at 0.2 centimeter to the mesenteric border and should never exceed the anti-mesenteric border . In case of large pancreas remnant, a longitudinal jejunum incision will be done at anterior part of anastomosis.The posterior part of anastomosis is two layers of intermittent suture, including seromuscular suture layer and full thickness suture layer. The anterior part of anastomosis is a single layer full thickness suture. At last, the seromuscular layer of the proximal jejunum is sutured with the anterior pancreatic capsule to cover the anterior part of anastomosis.

6.2 STUDY INTERVENTION COMPLIANCE

The compliance will be assessed by the records of the follow up information.

6.3 CONCOMITANT THERAPY

For this protocol, a prescription medication is defined as a medication that can be prescribed only by a properly authorized/licensed clinician. Medications to be reported in the Case Report Form (CRF) are

concomitant prescription medications, over-the-counter medications and supplements. The use of somatostatin, somatostatin analogs, antibiotics and acid inhibitors should be recorded.

7 STUDY INTERVENTION DISCONTINUATION AND PARTICIPANT DISCONTINUATION/WITHDRAWAL

7.1 DISCONTINUATION OF STUDY INTERVENTION

Discontinuation from SMMP does not mean discontinuation from the study, and remaining study procedures should be completed as indicated by the study protocol. If a clinically significant finding is identified (including, but not limited to changes from baseline) after enrollment, the investigator or qualified designee will determine if any change in participant management is needed. Any new clinically relevant finding will be reported as an adverse event (AE). The data to be collected at the time of study intervention discontinuation .

7.2 PARTICIPANT DISCONTINUATION/WITHDRAWAL FROM THE STUDY

Patients can withdraw from the trial at their own request or at the request of their legal representative at any time. Patients may be removed if, in the investigator's opinion, continuation of the trial could be detrimental to the patient's well-being or if a PD is not performed due to technical unresectability, metastatic disease, or other reasons. Every withdrawal will be recorded in the clinical report forms (CRFs) and in the patient's medical case records. All examinations scheduled for the final trial day will be performed on all patients and documented. All data will be analyzed according to the intention-to-treat (ITT) principle.

7.3 LOST TO FOLLOW-UP

A participant will be considered lost to follow-up if he or she fails to return for scheduled visits on 3 weeks and 3 weeks after the operation is unable to be contacted by the study site staff.

The following actions must be taken if a participant fails to return to the clinic for a required study visit:

- The site will attempt to contact the participant and reschedule the missed visit and counsel the participant on the importance of maintaining the assigned visit schedule and ascertain if the participant wishes to and/or should continue in the study.
- Before a participant is deemed lost to follow-up, the investigator or designee will make every effort to regain contact with the participant (where possible, 3 telephone calls and, if necessary, a certified letter to the participant's last known mailing address or local equivalent methods). These contact attempts should be documented in the participant's medical record or study file.
- Should the participant continue to be unreachable, he or she will be considered to have withdrawn from the study with a primary reason of lost to follow-up.

